7.3 Product Label

A label will identify the batch, blood group and purity of the corresponding fraction collected (see Figure 7-3). The label will indicate the date and end time of processing, the unique isolation process number, the date and time of expiration of the preparation for transplant use, the donor identification (UNOS #), the recipient identification (UIC patient's personal medical record number and study ID if applicable), donor and recipient name and blood type. The label will further indicate the specifications *UNOS donor, for use by intended recipient only, human islets for transplant, biohazard* and

Caution: Biohazard Human Tissue, Sterility Testing has not been completed, heparin content and For Investigational Use Only.

[figure not shown]
Figure 7-3. Islet Transplant Label at UIC

	
UIC CELL ISOLATION FACILITY
 
HUMAN ISLETS FOR TRANSPLANT
 
ISLET LOT #: _____
		

COLLECTION DATE AND TIME
 
____/____/____ ____:____
 
month day year hour minutes
		
EXPIRATION DATE AND TIME (6H AFTER FILLING)
 
____/____/____ ____:____
 
month day year hour minutes
	

_____ ml settled volume of Islet Cells
 
_____ IEQ, Total Islet Equivalent # in bag
 
_____ ml Total Volume of Final Product
		
Bag _____ of _____
 
Contain Heparin, Total Units: _____
 
Store at Temperature of 16-24 °C
	

Recipient Name: _____
 
Recipient Medical Record #: _____
 
Recipient Study ID: _____
 
Recipient ABO/Rh: _____
		
Donor Name: _____
 
Donor UNOS: _____
 
Donor ABO/Rh: _____
 
ABO compatible: _____
	

BB – IND 9336
 
New Drug Limited by Law to investigational use ONLY
		
Caution: Biohazard Human Tissue
 
Caution: Sterility Test has not been completed
	

7.4 University of Illinois at Chicago Islet Processing Facility

The University of Illinois at Chicago has designed and constructed a certified and validated 1,000 clean room to allow for the production of allogeneic human islets for transplant. The Islet Processing Facility is located in the basement of the UIC Medical Center at [name].

Figure 7-4. Overall Plan of the UIC Islet Processing Facility

The clean room is 800 square feet in size and serviced by two dedicated air handling units and two refrigeration condensing units supplied by Trane Company. All air is 100% single pass and filtered via ducted filters, filtra LF panel and HEPA filters. The clean room is designed to adhere to Good Manufacturing Practice (GMP) regulations.

[figure not shown]
Processing is performed in four class 100 Nuair laminar flow bio-safety cabinets, two inside the main processing area and one located within the cold room (mentioned below). The clean room is positively pressurized with the processing room being the area of greatest pressure. Room pressures are monitored via a bank of Magnehelic differential pressure gauges. Rooms are air-locked and doors are equipped with magnetic locks to ensure only one door may open at a given time within the same space.

The clean room and hoods are certified bi-annually. Maintenance checks of lighting, air handlers, and Magnehelic gauges are also performed at this time. In addition, a thorough, intensive cleaning is performed on defined quarterly and annual schedules to supplement the routine day-to-day cleaning of the room. Routine environmental monitoring for viable and non-viable particles is performed under both static and dynamic conditions according to SOP.

Installation qualification (IQ), operation qualification (OQ), and performance qualification (PQ) have been performed during qualification runs to validate all critical equipment including hoods, centrifuges, and incubators, and are documented in individual equipment logs. All equipment is regularly checked and calibrated by a professional. Weekly equipment checks are performed on critical equipment to ensure consistent performance. All critical systems are constantly monitored for temperature and humidity by a central computer. Facility users are paged by the computer if values go outside of expected parameters.

Traffic of materials and personnel is carefully restricted in a clean in, dirty out manner. Gear will be wiped down and staff will don clean room gowning material consisting of mask, Tyvek suit, gloves, hairnet, shoe covers, and eye protection upon entering the facility through the defined entrance. After islet processing, gear and staff will exit via the defined exit only.

Figure 7-5. UIC Islet Processing Facility

Located within the clean room is a refrigerated cold room. This space is designated for use in the purification of islet cells. Islets will be separated from unwanted exocrine tissue through use of a COBE 2991 cell processor which must be refrigerated while

islets are inside. The cold room is used to accomplish this. The cold room is equipped with two refrigeration units operating independently of the clean room. The air within the cold room is HEPA filtered.

7.5 Quality Program

7.5.1 Facility Controls

Cleaning

The Islet Processing Facility manager is responsible for ensuring that personnel responsible for cleaning and sanitizing the Islet Processing Facility clean room are appropriately trained, and that there is compliance with the cleaning protocol. Cleaning is performed according to controlled SOPs. Routine cleaning is carried out following each islet isolation or at a minimum weekly. More thorough cleaning is performed on defined quarterly and annual schedules. All cleaning and/or sanitizing for each clean room facility or clean room equipment is documented on the appropriate log sheet.

Environmental Monitoring

Environmental monitoring is performed weekly under static conditions. In addition, dynamic environment testing is performed weekly with the first pancreas processed in a given month.

Environmental monitoring includes particle counts, airborne microbe sampling, and contact plate cultures in the facility, as well as monitoring sterile gloves worn by personnel in contact with the pancreas.

Equipment

All equipment is operated according to SOPs describing operation, cleaning, maintenance, and calibration. Installation qualification where possible, operation qualification, and performance qualification have been performed on all critical equipment. Lab staff makes weekly checks of all equipment used in isolation and/or storage. Checks are recorded along with associated charts, printouts, etc. in equipment log books. All thermometers and mechanical equipment are calibrated and/or certified annually. Calibrations and certifications are documented in individual equipment logbooks. BSC and air handling units are recertified semi-annually by an outside vendor, including HEPA filter integrity testing.

Documentation

All activities required for production and maintenance and control of the facility occur according to written procedures and systems and are documented in related logs. SOPs are organized into the following categories: Contracted Company SOPs, Program Definitions, Quality Assurance, Documentation, Isolation Procedure, Quality Control Batch Release, and Archived SOPs. All documentation related to islet isolation occurs on the Isolation Record. This involves records relating to traceability of product from receipt of pancreas to final distribution of tissue, including donor information, media

tracking information, processing information, notes during processing, QC sampling and results, verification of final product acceptability before release. The final distribution of tissue is recorded. When tissue is transplanted, the recipient's medical record number is logged in the Isolation Record under distribution. The isolation batch number is also recorded in the recipient's medical record. All records will be kept for 10 years in a locked file cabinet in the Islet Processing Facility manager's office.

Gowning

Prior to entry to the facility all staff will gown in Tyvek suits, hairnets, gloves, masks, eye protection, and shoe covers. All gowning occurs in a clearly defined area in the entrance vestibule. This area is clearly marked on the ground with white tape. Only fully gowned persons are permitted across the tape.

[figure not shown]
7.5.2 Quality Control Testing

The UIC Quality Control Laboratory (QC Lab) is located directly outside of the clean room exit. All QC testing for release is done in this lab. Appropriate protocols are in place for each test performed including glucose static incubation, islet quantification, viability staining, and endotoxin. *In vivo* quality testing of islet function by transplanting human islets into diabetic nude mice is performed in the UIC animal facility. Results are available only retrospectively. Quality Assurance, such as quarantine and/or release, equipment checks, critical equipment monitoring, etc., is performed in much the same manner as in the clean room. The QA specialist oversees the QC Lab and coordinates QC and QA for the Quality Program. All QC results are reviewed by [name] or an official designee prior to release of islets for transplant and are audited by the QA Specialist weekly.

7.5.3 Quality Assurance

Personnel Organization

Figure 7-6. The Organizational Chart for the Islet Processing Facility

The Cell Isolation Program is attached to the Department of Surgery and the Division of Transplantation at the University of Illinois Medical Center at Chicago. [name] is the Chief of Division of Transplantation and the Director of the Cell Isolation Program. He will direct all matters involving the program. The Quality Assurance Manager is responsible for regulation of processing general in-house QA. His/her responsibilities include but are not limited to ensure proper documentation, sign off on SOPs, Transplant Release Checklists, QC reports and raw material release form, Quality Assurance and environmental monitoring. The Assistant Director of Operation and Process Improvement direct all operational matters in both research and processing labs. His/her responsibilities include but are not limited to coordination, scheduling, staff training and maintaining the compliance to federal regulations. The Quality Control Laboratory is overseen by the Assistant Director of Operation and Process Improvement. All QC required for release will be performed in this area.

The Assistant Director of Operation and Process Improvement is responsible for training and directing technical and support staff. Technical Staff perform technical assignments as needed by following established protocols, and report to the Assistant Director of Operation and Process Improvement for all day-to-day operations of the facility. These operations include working in isolations on an on-call basis, performing quality assessment on the isolated islets, and filing proper documentation during and after each isolation. A minimum of four staff members are involved in an isolation. [name] or an official designee will supervise all activities during an isolation.

The Quality Assurance Manager will conduct a weekly review of the Isolation Records from the previous week. All records will be checked for completion, consistency, legibility, and accuracy. Specific attention will be paid to release testing. The Quality Assurance Manager will also conduct a quarterly audit of all Islet Processing Facility practices. Logbooks, protocols, and other documents will be reviewed at this time. The Quality Assurance Manager will submit all weekly and quarterly observations to the Program Director. The Quality Assurance Manager does not participate in any processing, and reports to an outside independent supervisor in order to avoid conflict of interest.

The facility Support Staff will assist in day-to-day operation of the facility. Secretarial, cleaning, and other support staff will perform their duties as assigned according to their job descriptions.

Training

Training is conducted by [name], the Chief of Operations, the Quality Assurance Manager, or a qualified, experienced staff member. All staff receive mandatory GMP clean room training at a minimum once per year. Staff must complete this training prior to participating in an islet isolation. Ongoing training will be conducted weekly at staff meetings. All participants in training sessions will sign in on a Training Form that will be kept in a training log in the Quality Assurance Manager's office.

Audits

Internal audits of the entire Quality Program will be conducted annually by an outside agency. These audits will be a system review of facilities, production, preventative and corrective action, compliance with SOPs, record keeping, and QC, training. Audits will be documented in a quarterly report that will be submitted directly to the Director of the Islet Processing Facility.

Ongoing review of the Quality Program will be conducted by the Quality Assurance Manager. There will be weekly checks of: preventative and corrective action, charting, QC, training, etc. Results will be documented in appropriate logs, and Discrepancy Reports will be generated when needed. Results of these checks will be communicated at weekly meetings with processing staff.

Additional audits may occur on an event-driven basis. In cases of adverse outcomes after transplant, unscheduled internal audits may occur at the discretion of the Director. Additional audits may be conducted by external federal and/or state agencies. Results of audits will be reviewed by the Director of the Islet Processing Facility, and changes will be made at his discretion and only with his approval. Occurrences of audits will be documented in the QA- Audit Log along with any notes or documentation associated with any audit.

SOPs are in place to support all QA activities. These SOPs are: Complaint Files, Corrective Action, Receipt of Supplies and Quarantine - Release of Media, Reporting Requirements, Training Program, QA Program Preventative Action, and Equipment Validation and Certification.

Deviation Control

Unexpected deviations from SOPs will be recorded in the Isolation Record. Equipment malfunctions will be noted in the logbook of the individual piece of equipment. Each deviation will also be recorded on a Discrepancy Form to be maintained in the Discrepancy Logbook, which will track the incident through its resolution. Corrective action(s) will be logged on the same form as the individual deviation. All deviations will be reviewed by [name] and the Quality Assurance Manager. Retraining of staff will be conducted when appropriate.

A planned deviation must be approved by [name] in advance of implementation and must be tracked in the Isolation Record. Planned deviations will also be reviewed by the Quality Assurance Manager.

Document Control

All processes and procedures are described in SOPs. SOP copies are located in the processing area and the Director's office, and one signed original is maintained in the Quality Assurance Manager's office. All staff will be trained in all SOPs. Changes to procedures will only be made by the Director or an official designee and must be signed and approved by the Quality Assurance Manager and Director. When a change occurs, outdated SOPs will be collected and staff will be re-trained. A copy of all outdated SOPs will be kept in the SOP file in the Quality Assurance Manager's office under Archived SOPs. SOPs are reviewed annually.

SOPs are given a unique identifying number consisting of the year separated by a hyphen from a three digit number and a version number. SOPs will be recorded in the SOP log in sequential number according to the three digit unique number between hyphens. For example, the first SOP to appear in the SOP log for 2003 will be SOP number 03-001-01. This means that the SOP was written in 2003, is the first SOP in the log, and is the first version of that SOP. In addition, all SOPs will have a suffix to designate the category of the protocol. This suffix will appear after a forward slash (/) in the SOP number section, e.g., 04-001-01/1.

All product batch documentation will occur in the Isolation Record. This record will trace the product from receipt through transplant and record all necessary data (dates, times, volumes, media information, etc.) in between. Each batch will be assigned an individual, unique number for traceability. All paperwork and testing results for each batch will be kept in an individual chart, numbered with the batch number. All charts will be kept in the locked office of the Quality Assurance Manager in a secure file cabinet. All charts will be kept for a minimum of ten years.

Additionally, all logbooks and associated paperwork will be located within the Quality Assurance Manager's office or within the facility when appropriate.

7.6 Product Testing

Samples of both product and transport media are tested at various points to monitor the process and provide information on the purity and safety of the product. Testing will be performed during and after islet production Quality Control 1 (QC1), and on the final product prior transplantation Quality Control 2 (QC2). See Table 7-3 for a complete list of product quality testing.

7.6.1 Quality Control Testing during and after Islet Cell Production (QC1)

During and after the islet isolation process multiple samples for QC are taken and tests are performed in the Quality Control Laboratory, LABS Inc. and the UIC Pathology Laboratory (see Table 7-3):

- Purity
- Yield
- Viability
- Endotoxin
- Bacteriology
- Glucose Static Incubation and Stimulation Index calculation. The result of this quality test will be determined retrospectively (post-transplantation) and will not be used as a quality release test. Rather, the result of this test will be correlated with the clinical outcomes.

7.6.2 Quality Control Testing of Final Product after Culture and before Transplantation (QC2)

After a minimum of 12h of culture and before transplantation multiple samples for QC are taken and tests are performed in the Quality Control lab, LABS Inc. and in UIC pathology laboratories (see Table 7-3):

- Purity
- Yield
- Tissue Volume
- Viability
- Endotoxin
- Bacteriology

- Bioassay by transplant into nude mice and Post-culture Glucose Static Incubation and Stimulation Index calculation. These quality tests will be performed retrospectively (post-transplantation) and will not be used as a quality release test. Data from this test will be collected and correlated with the clinical outcomes.

Table 7-3. Product Quality Testing

Test	Parameter and Test Method	QC Time Point
Purity	Dithizone-staining and determination of acinar-free islets using visual examination under microscope by qualified personnel	QC1 QC2
Islet Yield	Dithizone-staining cell size and enumeration evaluation using light microscopy with visual examination by qualified personnel	QC1 QC2
Tissue Volume	Tissue volume is estimated using a glass pipette or by visualization of centrifuged pellet.	QC2
Viability	Fluorescent dye method using fluorescein diacetate and propidium iodide with visual examination by qualified personnel	QC1 QC2
Endotoxin	Endotoxin unit (EU) content by Endosafe® Portable Test System with disposable cartridges, version 7.09, Charles River Laboratories	QC1 QC2
Bacteriology	Anaerobic, aerobic, and fungal growth as well as Gram staining are performed by qualified personnel in the UIC Pathology Laboratory	QC1 QC2
Glucose Static Incubation and Stimulation Index calculation	In vitro insulin secretion under low and high glucose stimulation. Insulin concentration evaluated by ELISA	QC1 QC2
Bioassay	Islets are transplanted into diabetic nude mice to determine function. Glucose and human c-peptide will be measured.	QC2

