6.5 Test Material and Administration

6.5.1 Islet Dosing and Administration

A minimum amount of islets of about 10,000 IE/kg recipient body weight is required for engraftment and confirmed C-peptide expression based on the Edmonton series. This form of procedure may require multiple transplants in order to reach this desired minimum number of islets, as previous clinical studies were unable to reliably reach insulin independence with a single transplant.

Eligibility for second or third islet infusion

Subjects are eligible for further transplant if by the end of the fourth week after the first islet infusion or by the end of the fourth week after the second islet infusion they do not meet insulin-independence criteria. If a subject does not reach the definition of insulin independence by the end of the third month after the third transplant, the subject may be considered for an exceptional fourth islet infusion. However, the indication for an exceptional fourth transplant needs to be presented to the Data Monitoring Committee and approval obtained.

Eligibility for islet retransplantation and/or fourth islet transplant:

Subjects are eligible for subsequent islet infusions if after a period of insulin independence of at least 30 days, they present with declining islet function requiring reintroduction of exogenous insulin. Subjects may receive this additional islet infusion anytime during the first year after the last islet infusion, or anytime during the 5-year follow-up, as long as no exclusion criteria are present and avoiding any HLAs (human leukocyte antigens) against which the recipient may have developed donor specific antibodies.

No maximum number of delivered islets is specified, except that the number must exceed 10,000 IE/kg following 2 islet transplants, and packed cell volume may not exceed 10 mL per transplant.

Transplant Procedure

Islets will be isolated from human pancreases procured from deceased multi-organ donors as described in Section 7. The islet isolation procedure will be performed in the clean room facilities of the Cell Isolation Laboratory at the University of Illinois at Chicago Hospital (see Section 7.4 *University of Illinois at Chicago Islet Processing Facility*). Isolated human pancreatic islets will be stored for a maximum of 12 hours before transplantation (see Section 7.2 *Product Manufacturing*).

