Cell sampling is done by drawing 1 mL of the reconstituted islet preparation into 15 mL conical tubes and diluted 1:10 with wash solution. Two tubes are prepared using islets of higher purity fraction and one tube with islets of the lower purity fraction. Refer to section 7.6.3 for an explanation of islet enumeration, which is designated by EIN (Equivalent Islet Number). The samples are then distributed as follows:

- 2 x 1 mL for islet counting (EIN) and determination of islet purity for each fraction
- 9 mL for islet viability from a higher purity fraction tube
- 1 mL for endotoxin testing from the lower purity fraction
- 5 mL for microbial culture and direct Gram staining in duplicate

The cell sampling is based on the assumption of having a minimal islet mass of 250,000 EIN for clinically useful preparations (5,000 EIN/kg for a 50 kg patient). Thus, 1 mL of the final preparation contains a minimum of 1,000 EIN and 1 mL of the 1:10 diluted contains a minimum of 100 EIN, which is a representative sample for quality control.

For microbial and endotoxin testing and direct Gram staining, supernatant and cellular components are mixed 45 mL supernatant with 5 mL of cell suspension for microbial testing and Gram staining, and 1 mL supernatant and 1 mL cell suspension for endotoxin testing. In this way we avoid losing too many islets for quality control while assuring a relevant sample for microbial and endotoxin testing as well as the direct Gram staining. Results of all tests will be available prior to release of the product.

Once the count is available, 400-600EI are taken and cultured for Glucose static incubation (GSI).

Human islets are then spun and re-suspended in culture media containing indicator-free CMRL supplemented according to SOP.. After one washing the islet preparation is plated in a non-adherent culture T175 flask and incubated under standard cell culture conditions in an incubator at 22-37° C with 5% CO₂, in order to avoid loss of the product due to attachment to the culture flask. The time of culture will be kept as short as possible and will not exceed 40 hours.

c. Preparation of Purified Islet Cells for Transplantation

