7.6.4 Criteria for Quality Control Testing

Islet purity, yield, tissue volume, viability, direct Gram staining, and endotoxin levels will be analyzed prospectively and will determine the decision whether a preparation can be released for transplantation. Bacterial and fungal growth, islet potency determined by glucose static incubation, and transplantation into nude mice are performed retrospectively. Acceptable parameters of quality control testing of the final product are summarized in Table 7-4.

Table 7-4 Acceptable Parameters of Quality Control Testing

QC test	Acceptable Parameters
Purity	≥ 50%
Yield	≥ 5,000 EIN/Kg
Viability	≥ 70% for high purity layer and >29% for combined preparation
Tissue Volume	≤ 15mL
Endotoxin	≤ 5 EU/Kg bodyweight of recipient
Bacteriology	Gram staining negative Aerobic growth negative Anaerobic growth negative Fungal growth negative
GSI and Bioassay	To be determined during the study, based on correlation with observed clinical outcomes

7.6.5 Action Plan in the Case of a Positive Sterility Result after Product Release

Since results of sterility testing are not available until after administration of the islets, a plan of action for patient notification and treatment in case of positive results in the sterility culture is in place. Any organism detected from the final implanted islet cell preparation will be further evaluated for species identification and antibiotic sensitivity and resistance, and the recipient of the preparation will be treated as medically indicated.

The PI will evaluate the recipient for signs and symptoms of infection. The PI will use vital signs, WBC, and blood cultures to screen for infection. If evidence of infection is found, the patient will be treated according to sensitivity of identified micro-organism(s) and monitored as required. Infection of the recipient by an islet preparation will be considered a serious adverse event, and the necessary action will be taken as described in Section 6.10.5 *Monitoring and Reporting of Adverse Events*.

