7.7.4 Comparison of Viability and Potency Over Extended Culture

The viability and potency of UIC and CIT manufacture over an extended culture are compared in table 7-7.

Table 7-7. Comparison of viability and potency of CIT (C###) and UIC (H####) manufacture over culture. **VB pre:** viability of pre-culture islet product in percentage; **VB post:** viability of post-culture islet product in percentage; **SI pre:** glucose stimulated insulin release index for pre-culture islets; **SI post:** glucose stimulated insulin release index for post-culture islets; **EIN pre:** pre-culture islet equivalent; **EIN post:** post-culture islet equivalent; **RV %:** percentage value of islets recovered post-culture; **CT:** culture time in hours

ID	VB pre	VB post	SI pre	SI post	EIN pre	EIN post	RV %	CT		ID	VB pre	VB post	SI pre	SI post	EIN pre	EIN post	RV %	CT
H309	96.76	97.30	5.02	—	521,903	328,954	63	12.5		C023	99.60	98.34	1.06	1.31	479,009	390,958	82	37.3
H318	98.22	94.88	2.12	—	609,221	365,496	60	12.9		C026	98.80	98.68	1.56	8.95	391,760	402,410	103	38.3
H319	94.94	95.22	4.69	—	472,899	474,444	100	11.8		C031	99.04	96.00	1.28	1.22	399,527	240,541	60	36.3
H321	92.42	93.90	3.2	—	480,117	474,376	99	14.0		C032	98.72	98.64	3.63	N/A	646,450	402,470	62	52.3
H331	95.50	94.12	2.45	—	394,386	385,412	98	11.7		C035	95.00	91.50	1.05	1.17	719,243	394,024	55	42.4
H355	98.02	99.00	4.89	—	435,186	398,745	92	9.7		C036	95.50	94.96	2.82	1.38	493,075	375,718	76	21.0
H368	95.96	97.88	1.44	—	797,357	539,285	68	18.0		C038	97.66	96.24	8.29	1.2	588,601	341,590	58	37.7
H370	95.46	97.00	—	—	495,653	312,179	63	23.0		C045	97.88	96.76	2.86	2.64	647,404	508,335	79	27.5
H379	96.16	96.14	2.42	—	1,300,903	858,856	66	8.5		C055	98.32	96.04	1.18	1.45	468,965	396,926	85	26.0
H380	96.90	93.06	2.14	—	535,618	376,999	70	14.2		C056	96.64	95.66	4.84	4.29	365,506	322,091	88	24.0
H386	94.06	95.58	1.95	—	673,261	505,748	75	9.3		C058	96.48	95.92	3.181	3.664	807,095	448,114	56	36.0
Av	95.85	95.83	2.73	—	610,591	456,408	75	13.2		Av	97.60	96.25	2.89	2.73	546,057	383,925	73	34.4
Sdv	1.69	1.83	1.21	—	256,033	152,282	16	4.2		Sdv	1.51	2.03	2.18	2.46	145,401	684,44	16	9.1

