7.8.3 Stability Data

For this investigational protocol, the islet preparation will be stored for a maximum of 12 hours under standard culture conditions in an incubator with 5% CO₂ at 37°C.

We investigated, as indicated in Table 7-5, the effect of 12 hours of culture on the EIN, viability, purity, and islet function of the islet preparation used for process qualification.

The number of islets (EIN) decreased by a mean of 20% (range from increase of 13% to decrease of 44%), whereas the viability increased by 7% (range from 0 to 15%), indicating that the mean net loss of viable islets during the storage period was 13%.

All glucose static incubation assays and mouse transplants were performed after a minimal storage period of 12 hours. The preparations remained sterile and the levels of endotoxins did not increase during the period of storage. The presented data indicates that the islets are stable during the 12-hour period of storage. During the proposed clinical trial, additional stability data will be collected from post-transplant samples including assessment of sterility, islet function, islet purity, and islet viability.

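### The protocol's hold-time limits for islets (12-hour maximum, 12-hour minimum, 40-hour maximum) agree only at exactly 12 hours, so a lot's deviation status cannot be determined.

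*Protocol*

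**What the plan says.** Four places in the protocol govern how long isolated islets may be held.

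- Section 6.5.1, Transplant Procedure: "Isolated human pancreatic islets will be stored for a maximum of 12 hours before transplantation".
- Section 7.8.3, Stability Data: "the islet preparation will be stored for a maximum of 12 hours under standard culture conditions". The sentence goes on to specify a 5% CO₂ incubator at 37°C.
- Section 7.6.2, on QC2 of the final product: samples are taken "After a minimum of 12h of culture and before transplantation".
- Section 7.2.2, at the end of the purification and culture step: "The time of culture will be kept as short as possible and will not exceed 40 hours". The incubator temperature given there is 22 to 37°C.

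Section 7.6.4 links testing to release: "Islet purity, yield, tissue volume, viability, direct Gram staining, and endotoxin levels will be analyzed prospectively and will determine the decision" on whether a preparation can be transplanted. Table 7-3 schedules tissue volume at QC2 only. Table 7-7 in Section 7.7.4 has a column CT, defined as "culture time in hours", for 11 UIC lots and 11 lots made by the CIT process.

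**The concern.** A maximum and a minimum set at the same value leave a single permitted time, which no manufacturing process can meet in practice. A third limit of 40 hours makes it unclear whether the 12-hour cap is meant to apply at all. Someone checking a lot held for 9 hours or for 18 hours would find one section that it satisfies and another that it breaks.

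What is at stake is limited but real. The trial is meant to support a biological license application (Section 6.2), and culture time is part of how the product is made. SAP Sections 6 and 7 call for listings of protocol deviations and of non-compliance with the transplant rules. A lot's hold time cannot be classified for either listing while the rule contradicts itself. There is also a question of support: the stability conclusion in 7.8.3 is drawn for 12 hours, while 7.2.2 permits more than three times that (40/12 = 3.3).

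**Working it through.** **Inputs.** Let t be the time in culture before transplant, in hours.

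- Sections 6.5.1 and 7.8.3: t ≤ 12.
- Section 7.6.2: t ≥ 12. It is written as a sampling time, but it binds the hold because the samples must precede transplant. At least one test that decides release, tissue volume, is scheduled only at QC2 (Table 7-3 with Section 7.6.4).
- Section 7.2.2: t ≤ 40.

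**Can storage and culture be separated?** If 6.5.1 meant something other than culture, the limits might coexist. Section 7.8.3 closes that route by describing the stored state as incubator culture.

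**Intersecting the limits.** The lower bound is 12 and the upper bound is min(12, 40) = 12, so the only common value is t = 12. This result needs only the two 12-hour limits. The 40-hour limit is compatible with the minimum and conflicts only with the 12-hour maximum. This is also the lenient reading: if the cap in 6.5.1 also runs through QC2 testing, filling and transport, a lot cultured for exactly 12 hours would already be over it.

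**Reproducing the plan's figures.** Table 7-7 gives a mean (SD) culture time of 13.2 (4.2) h for UIC and 34.4 (9.1) h for CIT.

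- UIC times: 12.5, 12.9, 11.8, 14.0, 11.7, 9.7, 18.0, 23.0, 8.5, 14.2, 9.3. Sum 145.6; mean 145.6/11 = 13.24; SD with n−1 = 4.18.
- CIT times: 37.3, 38.3, 36.3, 52.3, 42.4, 21.0, 37.7, 27.5, 26.0, 24.0, 36.0. Sum 378.8; mean 378.8/11 = 34.44; SD with n−1 = 9.12.

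Both rows agree with the table.

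**UIC lots against each limit.**

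| Limit | UIC lots meeting it |
|---|---|
| t ≤ 12 (6.5.1, 7.8.3) | 5 of 11 |
| t ≥ 12 (7.6.2) | 6 of 11 |
| t ≤ 40 (7.2.2) | 11 of 11 |
| All three | 0 of 11 |

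**Coverage of the stability data.** The conclusion in 7.8.3 rests on 12-hour observations from five qualification isolations (Table 7-8). Table 7-7 adds viability and recovery for UIC lots at 8.5 to 23.0 h, but its post-culture stimulation index column holds only dashes for UIC. Times beyond 23.0 h in that table, up to 52.3 h, come only from the CIT process.

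**The case against.** The strongest reply is that little depends on this. Release is defined in Table 7-4 by purity, yield, viability, tissue volume, endotoxin and bacteriology; hold time is not a criterion. QC2 repeats the count and viability after culture, so islets lost during the hold are seen before infusion. No SAP efficacy analysis uses hold time. All of this stands. A reader might infer that the release status of each lot is undefined, but the documents do not support that. Only deviation status is unclear.

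Other tempting inferences also go too far:

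- *That the protocol has no data past 12 hours.* Table 7-7 has them. Mean post-culture viability is 95.83% (UIC, mean 13.2 h) and 96.25% (CIT, mean 34.4 h), and mean recovery is 75% and 73%. The comparison is uncontrolled, but it shows no obvious extra loss with longer culture.
- *That the mean 20% fall in islet number in 7.8.3 measures the harm.* That fall is at 12 hours, the one time that satisfies every limit. Section 7.8.3 offsets it with a 7% rise in viability, for a net loss of 13%. Sections 7.8.1 and 7.8.2 say that the organs were of research quality.
- *That the CIT lots breach this protocol.* Sections 7.7 and 7.7.4 place them under a different IND (BB IND9336).
- *That hold times go unrecorded, or that longer-hold stability data are on the way.* Section 7.5.3 already has the Isolation Record capture dates and times from receipt to transplant. Section 7.8.3 promises further stability data but does not mention longer holds.
- *That the two temperatures exclude each other.* 37°C lies inside 22 to 37°C. The wording differs, but both can be met.

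None of these points removes the clash between the 12-hour maximum and the 12-hour minimum, and no section reconciles it.

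**Conclusion.** The concern holds as an internal inconsistency. Sections 6.5.1 and 7.8.3 cannot be followed together with 7.6.2 except at exactly 12 hours, and 7.2.2 contradicts the 12-hour cap. The consequence is that whether a lot's hold time is a deviation cannot be determined.

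The size is best shown by the UIC lots in Table 7-7: 6 of 11 were over 12 hours, 5 of 11 under, and none met every limit. This describes historical practice. A reader might take it as evidence of past deviations, but the documents do not say that these lots were held under the current wording.

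On support, the 7.8.3 conclusion reaches 12 hours, and the UIC data on viability and recovery reach 23.0 hours without post-culture function. The rest of the range up to 40 hours is covered only by lots from the other process.

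The verdict rests on two readings: that storage in 6.5.1 is the incubator culture described in 7.8.3, and that QC2 must be sampled before a lot is infused. The text supports both. The documents do not show which limit was intended.

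**What to change.** Reconcile Sections 6.5.1, 7.2.2, 7.6.2 and 7.8.3 to one hold-time rule. State when the clock starts and stops, in particular whether testing, filling and transport count. Align the 37°C and 22 to 37°C wording at the same time. Next to the rule, name the stability data that support it, by table and by process (UIC or CIT), and say where post-culture function was not measured. The choice of limit belongs to the sponsor, and none is suggested here.

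The cost is a wording amendment. No new recording is needed, since batch times are already captured, and no SAP analysis changes. If the rule chosen goes beyond what the cited data cover, further stability data would be an additional cost that the documents do not show as already planned.
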